1. PREFACE

This SAP describes the planned analysis and reporting for the Recovery after Stress Toolkit (RESET) Trial.

The reader of this SAP is encouraged to also read the clinical protocol for details on the conduct of this study, and the operational aspects of clinical assessments and timing for completing a patient in this study.

2. PURPOSE OF SAP

This SAP is important for the following reasons: (1) to ensure that data collected in the study are adequate to address the study hypotheses; (2) to prevent ad hoc decisions in analyzing study data; and (3) to prospectively identify a timeline and structure for completion of study analyses. The planned analyses identified in this SAP will be included in future manuscripts. Also, exploratory analyses not necessarily identified in this SAP may be performed to support the clinical development program. Any post-hoc, or unplanned, analyses not identified in this SAP performed will be clearly identified in subsequent versions.

2.1 SAP VERSION HISTORY

After a version of an analysis plan is approved for use in a study (for example, by a Data Safety Monitoring Board or study Principal Investigator), any subsequent changes to the SAP require a subsequent version of the SAP to be released. Each such subsequent version of the SAP must explicitly summarize all changes made in each SAP revision since the initially approved version. This section of the SAP contains that summary. All previous approved SAP versions must be archived and should be easily accessible for review if needed.

3. STUDY OBJECTIVES AND ENDPOINTS

3.1 Study Objectives

3.1.1 Primary Objective

The primary objective is to compare the effect of cognitive behavioral therapy (CBT) delivered via telehealth to usual care among children with post-traumatic stress symptoms. We hypothesize that CBT will decrease symptoms compared to usual care.

3.1.2 Secondary Objectives

Secondary objectives are to demonstrate that CBT delivered via telehealth is feasible and acceptable.

3.2 Study Endpoints

3.2.1 Primary Endpoint

The primary outcome is post-traumatic stress symptoms (PTSS) as measured by the Child PTSD Scale (CPSS) at approximately 10 weeks post randomization. The CPSS will be provided by both parents and children. Children have a tendency to underreport their symptoms, and parents don't always notice their children's symptoms. As a result, the primary outcome of 10 week CPSS score will be calculated as the sum of the maximum of each individual question response across parent/child question dyads. If either the parent or child is missing the response for a given question, the only response available will be utilized. There is a precedence for this approach in the field.

3.2.2 Secondary Endpoints

The secondary outcome is CPSS at approximately 6 months post randomization.

3.2.3 Exploratory Outcomes

Key exploratory endpoints include: PROMIS-psychological stress; PROMIS-SF depression; SCARED (measure of anxiety).

We will also look at child and parent report CPSS at 10 weeks and 6 months post randomization.

The following tables include all outcomes collected for the study. Note that only

the ones mentioned above will be analyzed in the primary manuscript for the project.

Γable 1: Stu	dy Measures	Timing of Assessment †						
			T1	T2	Weekly	15	16	
Construct	Questionnaire	# of Items	1 week post-injury	1 month post-injury	during intervention	10 weeks post- randomization	6 months post- randomization	
Psychol	logical Health							
Screener	Acute Stress Checklist for Kids (ASC-Kids)	10	С	С				
Primary Outcome	Child PTSD Scale (CPSS)	24	В	В	С	В	В	
	Children's Post-Traumatic Cognitions Inventory (CPTCI) SF	10	С			С		
	Screen Child Anxiety and Related Emotional Disorders (SCARED)	41	С			С		
	PROMIS Scale – Anger SF	5	В			В	В	
	PROMIS Scale – Anxiety SF	8	В			В	В	
omorbid	PROMIS Scale – Depression SF	8	В			В	В	
Psychological Health and	PROMIS Scale – Psychological Stress SF	8	В			В	В	
Coping	PROMIS Scale – Physical Stress SF	8	В			В	В	
	Connor-Davidson Short Form	10	С			С		
	Traumatic Events Screening Inventory (TESI)	24	С			С		
	COVID-19 Life Impact (Child)	1	С					
	Vanderbilt ADHD Diagnostic Rating Scale (VADRS)	40	Р			P		
Physical	l Health							
	PROMIS Scales: Global Health ¹¹⁷	7	В			В	В	
	PROMIS Scale - Sleep	26	P			Р	P	
HRQoL								
	PedsQL4.0119	15	P			P	P	
End of tr	reatment surveys			•				
	System Usability Scale (SUS)	10				В		
	Satisfaction survey	33				В		

Table 2: Family Study Measures			Timing of assessment			
			T1 1 week	T2 1 month	75 10 weeks	T6 6 months
Construct	Questionnaire		post- post- post-			post-
Demographics	Parent demographics form	8	Р			
Social Support	Social supports	10	Р			
Family Functioning	McMaster FAD 120	12	Р			
	PROMIS Adult Self-Report Profile 29 v2121	29	Р		Р	
Parent Psychological Health	COVID-19 Exposure and Family Impact Survey (CEFIS)	37	Р			
	PTSD Checklist-DSM 5122 (PCL-5)	20	Р		P	

3.2.4 SAFETY OUTCOMES

Given the nature of the intervention we do not anticipate adverse events (AEs).

Serious Adverse Event (SAE): A serious adverse event (SAE) for this population is an adverse event that:

• results in death; or

- is life-threatening (the patient was, in the view of the site investigator, in immediate danger of death from the event as it occurred); or
- requires inpatient hospitalization or prolongs an existing hospitalization;
 or
- results in persistent or significant disability or incapacity; or
- any other event that, based upon appropriate medical judgment, may jeopardize the subject's health and may require medical or surgical intervention to prevent one of the other outcomes listed in this definition.

SAEs are collected according to our standard database form (see "AE_form_5-1-23.docx" form rc aesae).

4. STUDY METHODS

4.1 Overall Study Design and Plan

RESET is a prospective, randomized, multicenter trial of pediatric patients who experienced a traumatic injury and developed post-traumatic stress symptoms (PTSS). Subjects were randomized to one of two study groups to receive either (1) 8 sessions of cognitive behavioral therapy (CBT) or (2) usual care. The main research question is whether CBT reduces PTSS symptoms relative to usual care at 10 weeks post randomization.

4.2 Selection of Study Population

Candidate children are screened at the time of hospitalization for traumatic injury, and then again at one month post discharge, with the latter screening determined whether they had sufficient PTSS to qualify for the study. Those who qualified with sufficient PTSS and consented to participate in the study were randomized to CBT or usual care.

4.3 Method of Treatment Assignment and Randomization

Randomization of children eligible after the second screen was conducted using permuted blocks with equal allocation to each arm stratified by center (UU, UT, CI) and age group (8-11yrs, 12-16yrs). The randomization protocol was developed by the statistical team and implemented via REDCap.

4.4 Treatment Masking (Blinding)

Blinding was not possible due to the nature of this behavioral therapy intervention.

5. SAMPLE SIZE DETERMINATION

Goal enrollment is 53 children per group (106 total). This will provide 80% power

at a 0.05 significance to detect an effect size of 0.5.

The following table indicates sample sizes per group and total sample size for our 2 arm study under different combinations of correlation and effect size. With a correlation between baseline and follow-up CPSS measurements of 0.55, and an expected large effect size of 0.5, we would have 80% power at a 0.05 significance level to detect this difference with 45 subjects per group (90 total). Expecting a loss-to-follow-up (LTF) rate of 15%, we would need to enroll 53 subjects/group or 106 total. These calculations are based on an ANCOVA model, and were conducted in PASS v 16.0.6.

correlations and effect sizes.						
					Sample Siz	e
			Sample Si	ze	Adjusted for	or LTF
	Effect	Adjusted				
Correlation	Size	SD	N/Group	Total N	N/Group	Total N
None	0.35	1.00	130	260	153	306
0.4	0.35	0.92	110	220	129	258
0.55	0.35	0.84	90	180	106	212
None	0.50	1.00	64	128	75	150
0.4	0.50	0.92	53	106	62	124
0.55	0.50	0.84	45	90	53	106

Table 3. Sample size calculations for different combinations of within subject correlations and effect sizes.

6. ANALYSIS POPULATIONS AND STUDY SUBJECTS

6.1 ANALYSIS POPULATIONS

The following analysis populations are planned for the studies:

- Intent-to-Treat Population (ITT): The ITT population includes all patients who are randomized. All randomized subjects are included and analyzed according to their randomization assignment. The ITT population will be used for the primary analysis.
- **Per-Protocol Efficacy (PP):** The PP population includes all patients in the Efficacy Population who received the therapy that they were randomized to and then completed the CPSS at approximately 10 weeks post randomization. For the CBT arm we require at least 4 of the 8 therapy session(s) to qualify.

- No attempt will be made to recruit caregivers while their child is unstable, e.g. vitals are abnormal, there are major complications, or death may be imminent. Children with multiple injuries are eligible to participate but their caregivers will not be approached until any interventions (surgery, casting, etc.) are completed.
- . The accident involved the death of child's family member or friend

Figure 1a-b. Recruitment and randomization of participants.

Unable to contact family

Family declined screening

[figure not shown]
Eligibility criteria evaluated

Eligible

Completed one-week surveys

Figure 1a. Consort diagram - Baseline enrollment

Figure 1b. Consort diagram – Main study enrollment

7. GENERAL ISSUES FOR STATISTICAL ANALYSIS

7.1 Analysis Software

All analysis will be performed using SAS® Software version 9.4 or later whenever possible. Other software packages, including R, STATA and StatXact®, may be used for particular specialized procedures.

7.2 Methods for Withdrawals, Missing Data, and Outliers

We do not expect an issue with loss to followup in our study. Since CPSS is defined as the maximum of the child and parent scores, then in the event that one of either a child or parent score is missing, the other will be used. This affords some protection from missingness for our primary outcome. However, we do expect that there will be outliers in terms of when the CPSS was collected. Given that this is a smaller study, we plan to include all available measurements. We will summarize the extent of mistimed measures in our study and check for differences by treatment arm.

MI will be implemented for our ITT analysis if there is notable missingness in 10 week CPSS or an imbalance in missingness between treatment arms. MI is particularly useful if there are auxiliary variables that are highly correlated with both the study outcomes and risk of missingness. We will include the following auxiliary variables: child and parent measures (Tables 1-2) and patient demographic factors (Table 3).

In the event that MI is used, we will generate 20 imputed data sets which contain imputed values of the primary CPSS outcome (if R is used, we will use the mice package). The imputation model will include the outcomes and all predictor variables including the randomized treatment assignment, auxiliary variables and the baseline level of CPSS.

We plan to include all CPSS post therapy follow-up measures, regardless of timing. At the time of writing (3/31/23) we have 4 subjects prior to 10 weeks (59-65 days) in the CBT arm (none in usual care) and 8 subjects after (78-96 days) in the CBT arm and 1 subject after (105 days) in the control arm due to an issue with REDCap programming that sent the post-therapy assessment at the finish of therapy instead of 10 weeks. The REDCap issue was corrected. Since more subjects come after the window in the CBT arm this introduces an anticonservative bias. We will handle this in two ways: adjusting for time since randomization as a continuous variable in our analysis (primary strategy) and dropping these kids from our analysis (secondary strategy). The downside to our primary strategy is that it assumes that recovery is consistent over time. In reality, it's likely that more recovery happens earlier, so that this would be a conservative approach (but if more recovery happened later, then this would potentially be anticonservative). Another downside is that reviewers will have a difficult time understanding our rationale – but it is defensible and potentially takes an

anticonservative bias and makes it conservative. The downside to the secondary strategy is a loss of power.

7.3 Multicenter Studies

Since randomization was stratified by center we will account for center in our analyses as a covariate or stratification variable (the same applies for age group).

7.4 Multiple Comparisons and Multiplicity

As there is a single primary endpoint for this study (10 week CPSS), adjustment for multiple comparisons will not be required for the primary analysis. Similarly, multiple comparison adjustment is not required for the main secondary endpoint as a single main secondary comparison of CPSS at 6 months has been defined.

All other analyses will be considered exploratory. Hence, analyses of additional endpoints will be performed on a comparison-wise basis unless the writing committees for specific manuscripts define multiple comparison adjustments during the publications process. Reports from this trial should, whenever appropriate, note the nature of endpoints reported (primary vs. secondary vs. exploratory) as well as relevant multiplicities of comparisons.

7.5 Planned Subgroups, Interactions, and Covariates

Randomization was stratified by center and age group, and thus center and age group will be included as covariates in our analyses as mentioned above.

Planned subgroup analyses include sex, age group, and injury severity.

Cut off for enrollment was 11+, but we will conduct an exploratory analysis using 15+.

Future publications will explore the following questions:

Exploratory questions include whether children's pre-injury psychological health (anxiety and depression) and parent PTSS symptoms at time of injury will modify the treatment effect. Thus, we will plan to examine these questions through interactions.

Another exploratory research question is the relationship between PTSS symptoms and children's and caregivers' pre-injury psychological adjustment and

family function. This question will be evaluated by examining these variables in exploratory models.

8. STUDY SUBJECTS

8.1 Disposition of Subjects and Withdrawls

All subjects who provide informed consent will be accounted for in this study. The frequency and percent of subjects in each population, study withdrawls, subgroups, and major protocol deviations will also be presented.

8.2 Protocol Deviations

We will summarize the number and % of subjects overall and by center with minor and major protocol deviations. See "Recovery After Stress Toolkit - ReSeT _ REDCap.pdf" form "rc_protocol_deviation" for a list of deviations.

8.3 Inclusion and Exclusion Criteria

The number and percent will be presented for subjects meeting each Inclusion and Exclusion Criteria. Generally, it is expected that the overall percentage will be 100% for inclusion and exclusion criteria, except when waivers are granted or when data review indicates that inclusion or exclusion criteria have been violated.

9. DEMOGRAPHICS AND OTHER BASELINE CHARACTERISTICS

9.1 Demographics

Table 3: Demographics					
Child					
Sex					
Age					
Race/ethnicity					
Grade in school	If summer – last completed grade				
Co-morbidities (ADHD, anxiety,	Requires treatment – yes/no				
depression, learning problems)					
Does your child have any illness that	Yes/no				
needs lots of doctor visits such as asthma					
or diabetes?					
Has your child been hospitalized in the					
past year?					
Family					
Number of adults in the home	Bottom level is $1 = if$ greater than $1 - ls$				
	there a second parent in the home?				

Number of children in the home including the injured child	Bottom level is 1
Respondent relationship to child	List – mother, father, grandmother, grandfather, aunt, uncle, other relative, non-relative guardian or foster parent
Family income	Slider bar?
Respondent education	Grade school, high school, some college, college or greater
Insurance	None, Medicaid/CHIP, Private, Military
Marital status	Married, partnered, never married, divorced
Respondent race/ethnicity	

9.2 Measurement of Treatment Compliance

The CBT arm consists of 8 therapy sessions, and we will summarize the distribution of sessions completed as n (%).

If there is an issue with treatment adherence, we will use an instrumental variables approach to estimate treatment effects under different treatment doses. The advantage of this approach over a per-protocol analysis is that it enables us to analyze patients according to their randomized assignment.

We will also examine the efficacy of CBT treatment in subgroups consisting of sex, age group and injury severity by including interactions between the indicator for CBT versus usual care and sex, age group and injury severity (where each interaction will be assessed in a separate model). Each interaction model will answer the question of whether the efficacy of CBT treatment differs by the subgroup, and it will also provide the efficacy estimates within each subgroup level.

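### The planned instrumental-variables adherence analysis can identify one averaged effect of CBT, not effects at different numbers of sessions

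*Combined protocol and SAP*

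**What the plan says.** The adherence analysis is in SAP section 10.1. It is conditional: it opens with "If there is an issue with treatment adherence", and no threshold for such an issue is given. In that event, "we will use an instrumental variables approach to estimate treatment effects under different treatment doses". The stated advantage over a per-protocol analysis is that "it enables us to analyze patients according to their randomized assignment", so the implied instrument is the randomised arm.

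The design supplies one randomised contrast. Section 4.1: "Subjects were randomized to one of two study groups to receive either (1) 8 sessions of cognitive behavioral therapy (CBT) or (2) usual care". Section 4.3 describes "permuted blocks with equal allocation to each arm". No child is randomised to an intermediate number of sessions.

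Dose appears in two other places. For the per-protocol population, section 6.1 says "For the CBT arm we require at least 4 of the 8 therapy session(s) to qualify". For compliance, section 9.2 says "we will summarize the distribution of sessions completed as n" and percentage. The SAP does not say whether dose in the IV analysis means a session count or a cut-off, and it names no estimand, dose-response form, further instrument or identifying assumption.

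**The concern.** Sessions completed, from 0 to 8, are the result of what families do after randomisation. A two-level instrument supplies one estimating equation, which yields one coefficient. The text nevertheless describes the product as effects at more than one dose and commends the method for respecting randomisation.

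The number of sessions needed is a practical question for anyone who delivers this therapy. Figures for several doses, presented as coming from an analysis by randomised arm, could be taken to have the protection of randomisation. Their differences across doses would in fact come from an assumption or from the choice of cut-off.

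**Working it through.** **1. The plan's own figure.** The SAP gives no number for the IV analysis. Its sample size (section 5) reproduces. The adjusted SD is √(1 − 0.55²) = 0.835. The normal approximation gives n = 2 × (1.960 + 0.842)² × 0.835² / 0.5², or 44 per group after rounding up. The noncentral t calculation gives the stated 45, and 45 / 0.85 = 52.9 gives the stated 53. Nothing below changes these figures.

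**2. What the instrument identifies.** Let Z be arm, D sessions and Y the 10-week CPSS. Assume that usual care receives no study sessions. For any single coding g(D) of treatment:

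IV estimate = [E(Y|Z=1) − E(Y|Z=0)] / [E(g(D)|Z=1) − E(g(D)|Z=0)]

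With g(D) = D this is an average effect per session. With g(D) = 1 when D ≥ k, it is a complier effect for that cut-off. If instead 2, 4 and 8 sessions each have their own effect, the data give only

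ITT = p₂β₂ + p₄β₄ + p₈β₈,

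which is one equation in three unknowns. A simulated two-stage first stage agrees: the intercept and three fitted dose indicators have singular values 1.04, 0.28, about 0 and about 0, so the rank is 2 where 4 is needed.

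**3. Reading doses off a straight line.** Attendance and effect here are assumptions: 20%, 20% and 60% of the CBT arm at 0, 4 and 8 sessions, and an ITT benefit of 0.35 SD.
- Mean sessions: 0.2 × 4 + 0.6 × 8 = 5.6. Slope: 0.35 / 5.6 = 0.0625 SD per session.
- Scaled: 4 × 0.0625 = 0.25 SD and 8 × 0.0625 = 0.50 SD.
- Plateau truth with the same ITT effect and the same slope: 0.35 / 0.8 = 0.4375 SD at both 4 and 8.
- Error if the plateau is true: 0.25 / 0.4375 − 1 = −43% at 4 sessions; 0.50 / 0.4375 − 1 = +14% at 8.

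Range: with 10%, 10% and 80% attendance, the mean is 6.8 sessions. The line gives 0.206 and 0.412 SD, and the plateau is 0.35 / 0.9 = 0.389 SD. The errors become about −47% and +6%.

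**4. Reading doses off repeated cut-offs.** Second assumed example: 10%, 15%, 25% and 50% at 0, 2, 4 and 8 sessions, and an ITT difference of −4.0 CPSS points.
- At least 1 session: −4.0 / 0.90 = −4.44
- At least 4 sessions: −4.0 / 0.75 = −5.33
- All 8 sessions: −4.0 / 0.50 = −8.00

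Only the denominator changes. These three values are the same whatever the true curve, including a flat one.

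**5. Different truths, same data.** In the same example, set the CBT means at 0, 2, 4 and 8 sessions to 18, 17, 14 and 12. The CBT mean is then 13.85 and the usual-care mean 17.85. Four curves reproduce all of these observed means, and each gives the same per-session IV estimate, −4.0 / 5.3 = −0.755:

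| True curve | Effect in those completing 4 | Effect in those completing 8 |
|---|---|---|
| Linear | −3.02 | −6.04 |
| Full effect from 4 sessions | −5.33 | −5.33 |
| Full effect from any session | −4.44 | −4.44 |
| Effect only at 8 | 0 | −8.00 |

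Scaling the slope reports −3.02 and −6.04 in every row. The curves differ only in what each attendance group would have scored without therapy, which is not observed.

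**The case against.** The strongest reply is that the phrase about doses is loose and need not mean separate effects. It could mean one per-session slope, or several IV runs under different definitions of treated, and both can be estimated. That is true, but neither supplies effects by dose. The slope becomes an effect at a given number of sessions only under linearity, which the SAP does not state and this instrument cannot test. The repeated runs produce a gradient by construction (step 4).

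A second reply is that interactions of arm with baseline covariates could serve as extra instruments. This stands as a limit on any flat claim of impossibility. They would need the further untestable assumption that dose effects do not vary with those covariates. None is planned, and with about 90 evaluable children they would probably be weak.

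A third reply concerns precision. With 45 per group and an adjusted SD of 0.84, the ITT standard error is 0.84 × √(2/45) = 0.177 SD. Treating attendance as fixed, the scaled 8-session value in step 3 has a standard error of about 0.25 SD (0.177 × 8/5.6), four times the 0.0625 SD error. This stands for 8 sessions. At 4 sessions the error is 0.19 SD against a standard error of about 0.13 SD.

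A reader might also infer that the trial's efficacy conclusion is compromised, or that the SAP commits to a table of effects by session count. The documents support neither. The analysis is conditional, success is judged in the ITT population (sections 6.1 and 10.1), section 7.4 classes analyses beyond the two main CPSS comparisons as exploratory, and no such table is described. The undefined trigger is a separate matter and does not by itself show that the analysis should be run whatever the adherence.

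**Conclusion.** The point holds for the supplementary adherence analysis. As planned, with randomised arm as the only instrument, it identifies one averaged effect, and the wording attributes to it something the design does not provide. This goes beyond missing detail, because each natural way of completing the plan gets its dose pattern from linearity or from the choice of cut-off.

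The size depends on attendance and on the true curve. In the assumed examples, a plateau truth makes the scaled 4-session effect 43% to 47% too small and the 8-session effect 6% to 14% too large. Moving the cut-off from at least 1 session to at least 4 raises the estimate by 20% (5.33 / 4.44) with no change in the data. These figures assume no study sessions in usual care, and all attendance distributions are illustrative.

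**What to change.** In section 10.1:
- Delete the phrase about different doses.
- Pre-specify one IV estimand, with randomised arm as instrument and the primary-model covariates: the complier average effect of receiving at least 1 session. The exclusion assumption is most plausible there, since it requires only that assignment has no effect on children who attend nothing. If a gamma, lognormal or tobit outcome model is adopted, say on what scale the IV effect is estimated.
- Report the SAP's own cut of at least 4 sessions as a sensitivity analysis. State that it assumes 1 to 3 sessions have no effect, and that it overstates the complier effect if they help.
- Label any per-session figure a weighted average that rests on linearity when scaled to a given number of sessions.
- State that results across cut-offs will not be presented as a dose-response.

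The cost is SAP wording and a little programming, since session counts are already to be summarised. Dose-specific figures would no longer be reported, but the design cannot identify them.
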